### **Background and Rationale**

Approximately 4% of people in the US are either deaf or hard of hearing, equating to more than 13 million people. Of these, approximately 12 million people over the age of 5 years have difficulty hearing normal conversation even when using a hearing aid. Hearing difficulties affect all age groups and present significant challenges in daily life. These challenges are particularly acute in healthcare settings, where miscommunication results in suboptimal treatment and can lead to serious and potentially life-threatening outcomes for patients. Errors in interpersonal communication are an important contributing factor in medical errors, and the wearing of surgical masks by healthcare personnel and patients increases the likelihood of miscommunication. The surgical mask is an essential item of personal protective equipment, preventing the transmission of infectious agents such as bacteria and viruses, but conventional surgical masks can muffle speech and prevent patients and healthcare workers with hearing difficulties from being able to lip read. Lip reading is an important visual aid to communication for everyone but is particularly important for those who are deaf or hard of hearing. Our goal is to complete the development of a transparent surgical N95 respirator mask that prevents infectious disease transmission and improves communication among healthcare personnel and patients with hearing impairment.

### **Objectives**

The investigators will recruit adult participants to complete a usability survey on a transparent surgical N95 respirator (i.e., FaceView mask) designed to improve communication. The study aims to gather participants' perceptions of the novel transparent surgical N95 respirator vs. a conventional surgical N95 respirator. Following fitting of the masks (up to 30 minutes wear time each), the participants will complete a questionnaire to provide their perceptions of fit, comfort, ease of use, and benefit to communication.

## **Study Design and Procedures**

For both objectives, participants will try on both the FaceView Mask™ and the conventional surgical N95 respirator in quasi-random order from participant to participant. The participants will be informed that both masks meet N95 standards. The participants will be fit tested for both masks to ensure that the appropriate size is used. Training for fit testing will be performed by trained FaceView Mask, LLC personnel using a standard fit testing kit (3M™ Qualitative Fit Test Kit, Sweet) and the PI (and hired graduate student) will apply this fitting technique to all participants. The participants will wear each mask for up to 30 minutes before completing the study survey. All surgical respirators will be immediately discarded after use. Important requirements before fit testing include:

- No participants with facial hair should be included in the fit testing study.
- All participants (test subjects and administrators) should view the video at <http://multimedia.3m.com/mws/media/992396O/3m-respirator-fit-kit-test-video.mp4> before beginning the study.
- Test subjects must not eat, drink (other than plain water), smoke, or chew gum in the 15 minutes preceding the test.

## **Study Population**

A goal of 200 participants is desired with a minimum of 125 to meet study targets. We will be contacting known persons (not cold contacts) with ability to share study brochure by e-mail:

- 1) across the UAMS campus (e.g., College Deans, Center Directors, Program Directors);
- 2) surrounding clinics;
- 3) American Sign Language interpreter education at the University of Arkansas at Little Rock (Program Director)
- 4) Arkansas School for the Deaf (Superintendent and/or Assistant to the Superintendent); and
- 5) Communications Plus+ Interpreter Services, Inc. (owner and operator)

In the event that recruitment numbers are low in Little Rock, AR, the PI has contacts in San Francisco, CA, Ann Arbor, MI, and Rochester, NY who belong to the healthcare community, Deaf and hard of hearing community, or both. If needed, recruiters at these three additional sites will be hired to recruit 25 participants per site. Approvals for IRB amendments will be sought, and if necessary, IRB approvals will be obtained at those additional sites.

## **Compensation**

The participants will each receive a \$25 gift card as compensation for their participation in the study. As the subjects' active participation in this study ends with the completion of the survey, there is no retention plan.

### Inclusion Criteria

- Study participants must be at least 18 years old, have no health conditions that would prevent them from safely wearing an N95 respirator (e.g., severe asthma, chronic obstructive pulmonary disease), read in English and communicate in English or American Sign Language, and be able to provide or arrange their own transportation to the study location.
- The ages of the participants are expected to reflect the demographics of the healthcare workforce from which they will be recruited (typically 18-65 years).
- There will not be any exclusion of subjects based on racial/ethnic background. It is expected that the races and ethnicities represented in these studies will reflect the overall demographics of the workforce involved.

### Exclusion Criteria

- Prospective participants with facial hair.
- Children are to be excluded from the proposed research project because the current FaceView Mask™ is designed for adults.
- Adults who are non-English communicators.
- Any adult with health conditions that would prevent them from safely wearing an N95 respirator (e.g., severe asthma, chronic obstructive pulmonary disease).

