### **Data Analysis**

As this is a product survey, and not a treatment or intervention project, all data will be reported using descriptive statistics in the aggregate.

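### The inclusion criterion admits adults who read English and communicate only in American Sign Language (ASL), but the exclusion list bars them

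*Protocol*

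**What the plan says.** The language rule appears twice in the Protocol.

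- **Inclusion Criteria.** Participants must "read in English and communicate in English or American Sign Language". Reading and communicating are separate requirements, and for the second ASL is offered as an alternative to English.
- **Exclusion Criteria.** The list bars "Adults who are non-English communicators". ASL is not mentioned, and the term for a communicator is not defined.

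Two other sections bear on who might be affected. Study Population lists among the contacts for circulating the brochure "Arkansas School for the Deaf (Superintendent and/or Assistant to the Superintendent", together with an ASL interpreter programme and an interpreter service. If local recruitment is low, it plans to use contacts at three further sites "who belong to the healthcare community, Deaf and hard of hearing community, or both". Objectives states that participants will report "perceptions of fit, comfort, ease of use, and benefit to communication".

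The SAP says nothing about eligibility. Like the Protocol's Data Analysis section, it states only that "all data will be reported using descriptive statistics in the aggregate".

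**The concern.** For one identifiable group the two lists give opposite answers. A screener who works from the inclusion list enrols an English-reading, ASL-only adult. A screener who works from the exclusion list turns the same person away. Exclusions normally override inclusions, so literal application bars these people even though the inclusion criterion was written to admit them.

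Two things are at stake. The first is the make-up of the sample. One of the rated qualities is benefit to communication, and the Background gives improved communication with people who have hearing impairment as the purpose of the mask. Under the literal exclusion, wearers who communicate only in ASL contribute no ratings. Because the results are purely descriptive, the people admitted define the population that the summaries describe.

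The second is consistency. The back-up plan would use hired recruiters at three sites with 25 participants each (3 × 25 = 75), possibly under separate IRB approvals. Each site could resolve the two bullets differently.

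**Working it through.** The plan gives no figure to reproduce, and no statistical calculation applies. The check is a logical comparison of the two criteria.

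**Inputs**
- Inclusion Criteria: the person reads English, and communicates in English or in ASL.
- Exclusion Criteria: the person is not an English communicator.

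**Setup.** Take adults who read English and are otherwise eligible. Let E mean that the person communicates in English and A that the person communicates in ASL.
- Inclusion met = E or A
- Exclusion met = not E
- Eligible = inclusion met and exclusion not met

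| Profile | Inclusion met | Exclusion met | Result |
|---|---|---|---|
| E and A | yes | no | eligible |
| E only | yes | no | eligible |
| A only | yes | yes | **conflict; barred if the exclusion is literal** |
| Neither | no | yes | not eligible |

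**Results**
1. The inclusion criterion alone admits 3 of 4 profiles.
2. Inclusion with the literal exclusion gives (E or A) and E, which reduces to E: 2 of 4 profiles.
3. With ASL deleted from the inclusion criterion, inclusion is simply E, which gives the same 2 of 4. Under the literal exclusion the ASL alternative therefore admits nobody.
4. If the exclusion is rewritten as not E and not A, it is the exact complement of the inclusion among English readers. The result is 3 of 4 profiles and no conflict.

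Only the A-only profile is in conflict. Interpreters and Deaf adults who also communicate in English are treated consistently.

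**What cannot be computed.** The documents do not say how many prospective participants are ASL-only. The stated target ("A goal of 200 participants is desired with a minimum of 125 to meet study targets") is not broken down by hearing status or language, so the four profiles cannot be weighted.

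**The case against.** The best defence is that the exclusion list is shorthand. Most of its entries restate an inclusion in the negative: children mirrors the age limit, and the health-condition bullet repeats the inclusion almost word for word. On that view the language bullet means anyone who fails the language requirement, and a team that wrote ASL into the inclusion criterion would be unlikely to turn an ASL user away. This is probably the intent, but it is not what the bullet says, and a screener would have to set aside one written criterion to reach it.

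A second defence is that every candidate must read English, so written English might count as communicating in English and the conflicting group might be very small or empty. The inclusion criterion, however, lists reading and communicating separately. If reading English were enough to make someone an English communicator, the ASL alternative would again add nothing.

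Several limits do stand:
- The 3 of 4 and 2 of 4 counts describe logical categories of unknown frequency and say nothing about the size of any bias.
- No subgroup analysis by language or hearing status and no hypothesis test is planned, so no planned test or subgroup result depends on this group.
- The recruitment sources give only modest support. The school entry names administrators who can pass on a brochure, and the Deaf and hard-of-hearing contacts belong to a contingency plan. Neither shows that ASL-only adults will come forward.

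These points limit the consequence. They do not remove the contradiction.

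**Conclusion.** The two criteria contradict each other for adults who read English and communicate in ASL but not in English. This is a rule that is wrong as written, not a missing detail: applied literally, it bars people whom the protocol expressly names as eligible.

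The effect is confined to one of the four communication profiles, and its size in participants is unknown. Excluded people can be replaced, so recruitment numbers need not suffer, and the study can still meet its objective with the deaf and hard-of-hearing adults who remain eligible. The harm is a possible narrowing of the sample and uneven screening, which is worth correcting because the correction is nearly free.

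The conclusion rests on the ordinary reading of the inclusion criterion, in which reading is distinct from communicating and ASL is distinct from English. It does not depend on any assumption about how common each profile is.

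**What to change.** Reword the language exclusion so that it mirrors the inclusion, for example: *Adults who cannot read English, or who communicate in neither English nor American Sign Language.* The reading clause repeats what the inclusion criterion already requires and could be dropped; the second clause is what removes the conflict. Use the same wording in any IRB submissions for the back-up sites.

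If the investigator does mean to exclude ASL-only adults, the inclusion criterion should be edited instead, by removing the ASL alternative, and the restriction should be stated when the ratings of benefit to communication are reported.

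The cost is a one-line protocol and IRB amendment, with no added procedures or participants.

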### **Risks and Benefits**

When testing surgical mask that makes contact with the skin of the wearer, there is the potential for study participants to experience an allergic reaction to the mask material.

N95-grade surgical respirators are designed to filter the air breathed by the wearer, and there is the potential for study participants to experience some restricted airflow.

The information obtained from the participants will not jeopardize them in any way and will be deidentified.

The information obtained through this product testing study will inform the final design of a novel transparent surgical N95 respirator that will improve communication among healthcare workers and patients. Therefore, the participants are likely to benefit from the product that the proposed research supports.

There are no transparent surgical N95 respirators currently on the market. Successful testing of the FaceView Mask™ surgical N95 respirator will lead to commercialization of this novel product to improve communication between healthcare workers and deaf patients in situations requiring the use of N95-grade surgical respirators (e.g., when there is a risk of exposure to respiratory pathogens). Healthcare workers with hearing difficulties and those working in noisy environments may also benefit from this novel surgical N95 respirator. The FaceView Mask™ is designed to improve communication and reduce the risk of medical errors. The inclusion of an antimicrobial coating on the FaceView Mask™ will provide additional protection against respiratory pathogens and reduce fomite

Title: *Product Testing of the FaceView Mask™: Usability Survey*

PI: *[name].*

transmission of these pathogens that may occur through handling of the mask by the wearer.

An understanding of the needs of healthcare workers with regard to this novel N95 respirator (e.g., size, shape, fit, and comfort) will improve the effectiveness of the design and lead to a significant advance in personal protective equipment (PPE).

### **Data Handling and Recordkeeping**

We will collect all data using RedCap, and completed surveys will not collect personal identifying information or PHI. Therefore, the data are already de-identified/anonymized and untraced back to the participant.

The PI will carefully monitor study procedures to protect the safety of research subjects, the quality of the data and the integrity of the study.

At the conclusion of the study, the data will be retained and remain deidentified/anonymous, and later destroyed in accordance with institutional policy.

### **Data Analysis**

As this is a product survey, and not a treatment or intervention project, all data will be reported using descriptive statistics in the aggregate.

### **Ethical Considerations**

This study will be conducted in accordance with all applicable government regulations and University of Arkansas for Medical Sciences research policies and procedures. This protocol and any amendments will be submitted and approved by the UAMS Institutional Review Board (IRB) to conduct the study.

This is a minimal risk study and a waiver of documentation of consent is requested. The research involves no more than minimal risk to the subjects and the only record linking the subject and the study would be the consent document and the principal risk is the breach of confidentiality.

The study team will recruit *via* word of mouth and by emailing the study brochure to people known to the study team. The study will be fully explained to the participant prior to engaging in any activities. All participants will be given a copy of the study brochure for their records. Study participation will be taken as agreement to participate.

### **Dissemination of Data**

Results of this study may be used for presentations, posters, or publications. The publications will not contain any identifiable information that could be linked to a participant.

Title: *Product Testing of the FaceView Mask™: Usability Survey*

PI: *[name].*

## Appendices

See survey instrument in Documents.

Title: *Product Testing of the FaceView Mask™: Usability Survey*

PI: *[name].*

Study Title: Product Testing of the FaceView Mask™: Usability Survey

Principal Investigator: [name].
Department of Audiology and Speech Pathology
College of Health Professions
University of Arkansas for Medical Sciences
[name]
[name]
[contact]
Email: [contact]

Study location: University of Arkansas for Medical Sciences
[name]
[name]

Data Analysis

As this is a product survey, and not a treatment or intervention project, all data will be reported using descriptive statistics in the aggregate.
